8.4 Subject Identification

Subjects will be allocated a unique study identifier on all study documentation. The only documents which will contain any personal details is the consent form and the Subject Identification Log, which are maintained by the Investigator or designated study staff. Their identification is a number attributed regarding the country, number of the site and number dedicated to inclusion. For example: 57-0001-0005: country number 57, centre number 1, inclusion number 5.

8.5 Wound Identification

Each study wound will be allocated a sequential number within the subject starting with number 1. For example, subject 57-0001-0005, Wound 01, Wound 02; subject 57-0001-0006, Wound 01, Wound 02.

9 STUDY PROCEDURES

The following section describes the study procedures and data which will be collected at each procedure for the duration of the study.

9.1 Procedure Diagram

9.2 Study Visits

After Informed Consent has been obtained, the following study procedures will be performed. All data is to be entered into the applicable Case Report Form (CRF).

9.3 Schedule of Events

A schedule of events is in the table below.

9.4 Enrolment of Subject with Multiple Wounds

Subjects with multiple wounds are allowed into study. Each wound that meets all wound-specific inclusion and none of the wound-specific exclusion criteria should be enrolled into study. The randomization occurs at the subject level. All study wounds for a specific subject will be treated with the same study device (e.g., all study wounds in a subject randomized to AQUACEL® Ag+ Extra™ will be treated with AQUACEL® Ag+ Extra™. No wound-level cross-over is allowed.

TABLE 9.3-1: Schedule of Events

	Visit 1 Day 1	Visit 2 Day 14 (+/- 2 days)	Visit 3 Day 28 (+/- 2 days)	Visit 4 Day 42 (+/- 2 days)	Visit 5 Day 56 (+/- 2 days)	Visit 6 Day 70 (+/- 2 days)	Visit 7 Day 84 (+/- 2 days)	Additional Visit	End of Study Visit [^]
Informed Consent	X								
Inclusion / Exclusion	X								
Demographics	X								
Medical History	X								
Concomitant Medication	X	X	X	X	X	X	X		X
Wound History	X								
Wound-QoL-14	X	X*	X*				X		X@
Wound debridement per usual practice	X	X	X	X	X	X			
Wound Assessment	X	X	X	X	X	X	X	X	X
Randomisation	X								
Decision to continue with randomised dressing or Standard of Care		X							
Randomised Dressing Application	X	X	X\$	X&	X&	X&			
Secondary Dressing Application#	X	X	X	X	X	X			
Apply compression therapy	X	X	X	X	X	X			
Adverse Events	X	X	X	X	X	X	X	X	X
Device Deficiency%	X	X	X	X	X	X	X	X	X

* Wound-QOL-14 will be completed following the completion of treatment with randomized dressing on Day 14 (+/- 2 days) or on Day 28 (+/- 2 days) if additional 14 days of treatment with the randomised dressing occurred.

@ Collect QOL-14 if the Additional Visit is Study Completion visit.

\$ Application of the randomised dressing after Visit 2 (14-day visit) at the discretion of the investigator.

& After day 28, the PI or delegate will continue treatment of the wound according to the clinical needs based on their evaluation of the wound. If an antimicrobial wound dressing is required, the dressing that was randomly assigned during the initial phase of the study can continue to be used

Secondary dressing to be applied at the discretion of the investigator.

% If applicable

^ If end of study visit is not Visit 7

10 Visits

After Informed Consent has been obtained, the following study procedures will be performed.

10.1 Visit 1: Screening and Baseline: Day 1

The following procedures and data are collected at Visit 1. All information on this visit is required. Missing data and assessments will be considered a protocol deviation.

- Obtain Informed Consent
- Inclusion and Exclusion Criteria Review and Documentation
- Demographics (Sex, Age, Height, Weight, BMI calculation, Ethnicity)
- Medical History (Cardiovascular, Respiratory, Gastro-Intestinal, Endocrine, Haematological, Musculo-skeletal, Neoplasia, Neurological, Immunological, Dermatological, Allergies, Psychological, and Other)
- Obtain Concomitant Medications (Medication Used, Route, Dose, Unit, Frequency, Indication, Start Date, Stop Date or Ongoing)
- Study Wound(s) Assessment
 - Duration of wound
 - Location of the wound (i.e., left/right leg, posterior/ anterior, medial/ lateral, etc.)
 - Wound size (measured in cm at the longest point and across the widest point)
 - Wound bed appearance
 - Exudate level, colour, and consistency
 - Condition of peri-wound skin
 - Maximum pain level on a scale of 0 to 10 within the last 24 hours
 - Level of odour on a scale of 0 to 10 for the study participants and mild/medium/strong for the clinician.
 - Therapeutic Index for Local Infections (TILI) score
- Wound-QoL-14
- Randomisation to either AQUACEL® Ag+ Extra™ or Cutimed® Sorbact®
- Randomised dressing application (Size and Lot Number)
- Apply compression per standard of care (documentation of type used)
- Documentation of the use of secondary dressings, if applicable

Each study wound in subject with multiple study wounds is assessed independently.

10.2 Visit 2: Day 14 (+/- 2 days)

The following procedures and data are collected at this visit. All information on this visit is required. Crossover to the non-randomized study dressing is not permitted.

- Review of concomitant medications, documenting any changes (medication used, route, dose, unit, frequency, indication, start date, stop date or ongoing)
- Wound assessment
 - Wound size (measured in cm at the longest point and across the widest point, as well as depth)
 - Wound bed appearance
 - Exudate level, colour and consistency
 - Condition of peri-wound skin
 - Maximum pain level on a scale of 0 to 10 within the last 24 hours

- Level of odour on a scale of 0 to 10 for the study participants and mild/medium/strong for the clinician.
- Therapeutic Index for Local Infections (TILI) score
- Number of days, since last visit, where compression was not applied (including documentation of reason for no compression)

A clinician decision is required at this visit regarding continuation of the randomised dressing (AQUACEL® AG+ Extra™ or Cutimed® Sorbact®) or transition to long-term management per standard of care. In subject with multiple study wounds the decision is made for each study wound separately. For example, one wound can be selected for Option 1 and another wound for option 3.

Option 1: An additional 14 days of treatment with randomised dressing (AQUACEL™ Ag+ Extra™ or Cutimed® Sorbact®) is required.

Option 2: Further treatment with randomised dressing is not indicated. The wound should be further managed per standard of care.

Option 3: Clinician determines that a non-standard of care treatment is needed. Treatment with the randomised dressing is discontinued.

Regardless of the option chosen, the subject remains in the study and is followed-up until the study exit (see section 8.2)

Once the decision has been made on the treatment option, the following information will be collected.

- Dressing application according to clinician decision (randomised dressing or other dressing) (name, size and lot number is recorded)
- Documentation of any additional products used
- Document any additional therapies
- Document and address any Adverse Events
- Document and address any Serious Adverse Events
- Number of intermediate visits where dressings were changed between scheduled visits (this is the number of times a subject received a new dressing since the last visit)
- Wound-QOL-14 (only if Option 2 or 3 has been selected).

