18.2	Statistical Approach for the Primary Endpoint	45
18.3	Statistical Approach to Secondary and Exploratory Endpoints	45
18.4	Sample Size Determination.....	45
18.5	Multiplicity	45
18.6	Randomisation	46
18.7	Statistical Populations.....	46
19	CONFLICT OF INTEREST	47
20	GOOD CLINICAL PRACTICE AND STATEMENTS OF COMPLIANCE	48
20.1	Ethical Approval	48
20.2	Protocol Modifications.....	48
20.3	Periodic Reviews	48
20.4	Insurance.....	48
20.5	Patients' Compensation.....	48
20.6	Principal Investigator, Coordinating Investigator(S), Investigational Sites and External Organisations	48
20.7	Public Registration and Publication	49
21	LITERATURE	50
22	GLOSSARY, ABBREVIATIONS & ACRONYMS.....	53

SYNOPSIS

Study Title	A clinical study to compare the performance of AQUACEL® Ag+ Extra™ and Cutimed® Sorbact® dressing in the management of patients with Venous Leg Ulcers over a 12-week period
Study Type	Post-market
Principal Investigator (PI)	[name].
Device(s) Under Investigation	AQUACEL® Ag+ Extra™ (Experimental Arm) and Cutimed® Sorbact® (Control Arm)
Sponsor	Convatec Limited, GDC, [name], United Kingdom
Purpose	The primary purpose of this study is to evaluate performance of AQUACEL® Ag+ Extra™ in comparison to Cutimed® Sorbact® in the progression of wounds towards healing.
Design	Randomised, active-controlled, open label, multi-centre, global study

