10.3 Visit 3: Day 28 (+/- 2 days)

The following procedures and data are collected at this visit. All information on this visit is required. Following this visit, if the wound has not healed, the type of the further treatment is per investigator discretion and it can include continuous application of randomised dressing (if per standard of care) and other standard of care and non-standard of care options. Regardless of the type of the treatment continuation chosen, the subject remains in the study and is followed-up until the study exit (see section 8.2)

- Review of concomitant medications, documenting any changes (medication used, route, dose, unit, frequency, indication, start date, stop date or ongoing)
- Wound assessment
 - Wound size (measured in cm at the longest point and across the widest point, as well as depth)
 - Wound bed appearance
 - Exudate level, colour and consistency
 - Condition of peri-wound skin
 - Maximum pain level on a scale of 0 to 10 within the last 24 hours

- Level of odour on a scale of 0 to 10 for the study participants and mild/medium/strong for the clinician.
- Therapeutic Index for Local Infections (TILI) score
- Number of days, since last visit, where compression was not applied (including documentation of reason for no compression)
- Dressing application according to clinician decision (randomised dressing or Standard of Care) (name, size and lot number is recorded)
- Documentation of any additional products used
- Document any additional therapies
- Document and address Adverse Device Events
- Document and address Serious Adverse Events
- Number of intermediate visits where dressings were changed between scheduled visits (this is the number of times a subject received a new dressing since the last visit)
- Wound-QOL-14 (only if not collected at Visit 2).

10.4 Visits 4 - 7: Day 42 thru 84 (every 14 days +/- 2 days)

The following procedures are performed and data collected at the intermediate visits (every 14 days +/- 2 days until day 84). All information is required.

- Review of concomitant medications, documenting any changes (medication used, route, dose, unit, frequency, indication, start date, stop date or ongoing)
- Wound Assessment
 - Wound size (measured in cm at the longest point and across the widest point, as well as depth)
 - Wound bed appearance
 - Exudate level, colour and consistency
 - Condition of peri-wound skin
 - Maximum pain level on a scale of 0 to 10 within the last 24 hours

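### The interim Wound-QoL-14 is taken at Day 14 or Day 28 according to an open-label treatment decision, so a between-arm comparison of it is open to bias if continuation differs by arm

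*Combined protocol and SAP*

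**What the plan says.** The synopsis and Section 4.2.3 list Wound-QoL-14 as exploratory. Every subject completes it at baseline (Section 10.1).

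At Visit 2, "A clinician decision is required at this visit regarding continuation of the randomised dressing". Option 1 continues the dressing for a further 14 days. Option 2 applies when "Further treatment with randomised dressing is not indicated", and Option 3 moves the wound to a treatment outside standard of care. Options 2 and 3 both end the randomised dressing. The questionnaire follows that choice:

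- Section 10.2 (Day 14): "Wound-QOL-14 (only if Option 2 or 3 has been selected".
- Section 10.3 (Day 28): "Wound-QOL-14 (only if not collected at Visit 2".
- Footnote * to Table 9.3-1: "Wound-QOL-14 will be completed following the completion of treatment with randomized dressing on Day 14 (+/- 2 days) or on Day 28", the latter when the extra 14 days of treatment took place.

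Section 10.2 adds: "In subject with multiple study wounds the decision is made for each study wound separately". It illustrates this with a subject who has one wound on Option 1 and another on Option 3.

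The last score is taken at Visit 7 or at study exit (Section 10.4). Exit comes early when all study wounds have healed, possibly between visits (Sections 8.3 and 10.6). The synopsis describes the design as "Randomised, active-controlled, open label, multi-centre, global study". Section 18.3 leaves the analysis of exploratory endpoints to the SAP, and the document supplied contains no SAP text on Wound-QoL-14.

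**The concern.** The day on which a subject is scored is decided after randomisation, by a clinician who knows the arm and has just assessed the wound. Subjects taken off the dressing are scored two weeks earlier than those kept on it. A between-arm difference in this score can therefore mix three things: the effect of the dressing, time since baseline, and who was judged ready or unsuitable to continue.

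Under these rules the scores that would separate them are not collected. A subject who stopped has no Day 28 score unless exit happens to fall then, and a subject who continued has no Day 14 score. The exit score is not a fixed-time substitute, because its timing depends on healing.

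At stake is the interpretation of one exploratory endpoint, and a loss of data that cannot be made good once subjects have passed Visit 3.

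**Working it through.** **Step 1. Who is scored when.**

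| Situation at Visit 2 | Day 14 | Day 28 |
|---|---|---|
| All study wounds on Option 2 or 3 | scored | not scored |
| All study wounds on Option 1 | not scored | scored |
| Mixed options, Sections 10.2 and 10.3 read literally | scored | not scored |
| Mixed options, footnote to Table 9.3-1 | randomised treatment still under way | scored |
| All wounds already healed and subject exited | exit score only | exit score only |

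The first two rows agree in all three places. The two mixed-option rows do not agree with each other.

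**Step 2. The plan's own figure.** No figure is given for Wound-QoL-14. The trial size in Section 18.4 is used below, so I checked it. Inputs: healing 0.80 in both arms, margin 0.15, one-sided alpha 0.05 (Section 18.2 uses a two-sided 90% interval), power 85%. Per arm, n = (1.645 + 1.036)² × 2 × 0.8 × 0.2 / 0.15² = 102.2, rounded up to 103. That is 206 in total, as stated, with 85.2% power at 103 per arm.

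**Step 3. What the timing rule does to the mean.** Suppose both arms have the same true course. Let p be the share continued and c the mean change from Day 14 to Day 28 among those continued. The mean recorded score is the Day 14 mean plus p × c, so the spurious difference between arms is p(E) × c(E) − p(C) × c(C).

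- If the decision is unrelated to quality of life, c equals the overall change g in both arms, and the difference is g × (gap in share continued).
- If the shares are equal but the criteria differ, the difference is p × [c(E) − c(C)], which need not be zero.
- If shares and criteria are both equal, it is zero.

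**Step 4. Size, with g and the gap assumed.** The documents give no Wound-QoL-14 mean, SD or continuation rate, so all values are in SD units. With 103 per arm, SE = √(2/103) = 0.139 SD. With t = difference / SE, the two-sided 5% false-positive rate is 1 − Φ(1.96 − t) + Φ(−1.96 − t).

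| Gap in share continued | Change g (SD) | Spurious difference (SD) | t | False-positive rate |
|---|---|---|---|---|
| 0 points | any | 0 | 0 | 5.0% |
| 20 points | 0.2 | 0.20 × 0.2 = 0.04 | 0.29 | 5.9% |
| 20 points | 0.3 | 0.20 × 0.3 = 0.06 | 0.43 | 7.1% |
| 20 points | 0.5 | 0.20 × 0.5 = 0.10 | 0.72 | 11.1% |
| 40 points | 0.3 | 0.40 × 0.3 = 0.12 | 0.86 | 13.8% |
| 40 points | 0.5 | 0.40 × 0.5 = 0.20 | 1.44 | 30.0% |

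**Step 5. A decision that depends on status.** A simulation (4,000 trials, 103 per arm, no true difference) let subjects with better Day 14 scores be more likely to stop. Assumptions: correlation 0.6 between Day 14 and Day 28 scores, correlation 0.5 between Day 14 score and the decision, g = 0.5 SD.

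| Share continued, by arm | Mean difference (SD) | False positives, planned timing | False positives, fixed Day 28 |
|---|---|---|---|
| 50% v 50% | 0.00 | 4.7% | 4.5% |
| 70% v 50% | 0.09 | 11.1% | 4.5% |
| 80% v 40% | 0.18 | 27.7% | 4.7% |

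With g = 0.2 SD, the planned-timing rates are 5.1%, 5.7% and 6.9%. Equal shares with different criteria were not simulated.

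**The case against.** The strongest reply is that both arms follow one rule. Scoring at the end of randomised treatment is a recognisable choice, openly stated in the footnote, and it distorts nothing if the arms are continued alike. That stands: nothing in the documents shows a gap in continuation, and with none the test keeps its level. Equal shares are still not a safe presumption. The Section 1.2 device table calls for the need for AQUACEL Ag+ Extra to be re-assessed after 14 days and has no matching statement for Cutimed Sorbact. That text follows a sentence on burns, so it is a reason for caution and not evidence of a gap.

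The sizes are also assumed, and the lower one is small: 0.06 SD is about 0.4 of a standard error. The 0.20 SD case needs a 40-point gap between two active dressings.

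A reader might infer that the plan compares the arms at different times and so yields a biased result. The documents do not support that. They fix when the score is collected, and the analysis is left to SAP text that is not supplied.

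A reader might also infer that no analysis could help. That is too strong. Baseline Wound-QoL-14 is available, and wound size, pain, odour and TILI score are required at Visit 2 whatever option is chosen. A model using these could reduce the distortion under a missing-at-random assumption. It could not reliably remove it, because Day 14 and Day 28 scores are not both observed in the same subject.

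Lastly, the mixed-option conflict rests on a literal reading. Section 10.2 does not say whether its condition means any wound or all wounds, and read as all wounds it would agree with the footnote. The number of subjects affected is unknown.

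**Conclusion.** The point holds as a risk of bias in one exploratory endpoint. The time of the interim score depends on a post-randomisation, open-label decision, and this is explicit in Sections 10.2 and 10.3 and in the schedule footnote. A between-arm comparison of that score is exposed if the share continued or the decision criteria differ by arm, and is not exposed if they are the same. Across the assumed range the spurious difference runs from 0 to 0.20 SD and the false-positive rate from 5% to 30%; no input to that range comes from the documents.

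Separately, the collection rule for subjects with wounds on different options must be reconciled between Sections 10.2 and 10.3 and the footnote.

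It would be wrong to extend the point to the trial's main conclusions. The primary endpoint, the secondary endpoints and the sample size of 206 do not depend on Wound-QoL-14.

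**What to change.** - Collect Wound-QoL-14 at both Visit 2 and Visit 3 from every subject still in the study, whatever option is chosen. Delete the conditional clauses in Sections 10.2 and 10.3 and amend the footnote to Table 9.3-1 to match. This also removes the mixed-option conflict. The end-of-treatment score can still be derived from the two visits.
- In the SAP, name Day 28 as the time of the between-arm comparison, adjusted for the baseline score. Day 28 matches the 4-week primary treatment period used for two secondary endpoints.
- State how subjects who healed and exited before Day 28 are handled, for example by using the exit score with a sensitivity analysis.
- Treat the exit score as descriptive, or account for its timing, which depends on healing.

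The cost is one extra 14-item questionnaire per subject, a few minutes at a visit already scheduled, plus a protocol amendment. Subjects stay in follow-up under every option, so no visit is added and clinical management does not change.

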10.3 Visit 3: Day 28 (+/- 2 days)

The following procedures and data are collected at this visit. All information on this visit is required. Following this visit, if the wound has not healed, the type of the further treatment is per investigator discretion and it can include continuous application of randomised dressing (if per standard of care) and other standard of care and non-standard of care options. Regardless of the type of the treatment continuation chosen, the subject remains in the study and is followed-up until the study exit (see section 8.2)

- Review of concomitant medications, documenting any changes (medication used, route, dose, unit, frequency, indication, start date, stop date or ongoing)
- Wound assessment
 - Wound size (measured in cm at the longest point and across the widest point, as well as depth)
 - Wound bed appearance
 - Exudate level, colour and consistency
 - Condition of peri-wound skin
 - Maximum pain level on a scale of 0 to 10 within the last 24 hours

- Level of odour on a scale of 0 to 10 for the study participants and mild/medium/strong for the clinician.
- Therapeutic Index for Local Infections (TILI) score
- Number of days, since last visit, where compression was not applied (including documentation of reason for no compression)
- Dressing application according to clinician decision (randomised dressing or Standard of Care) (name, size and lot number is recorded)
- Documentation of any additional products used
- Document any additional therapies
- Document and address Adverse Device Events
- Document and address Serious Adverse Events
- Number of intermediate visits where dressings were changed between scheduled visits (this is the number of times a subject received a new dressing since the last visit)
- Wound-QOL-14 (only if not collected at Visit 2).

10.4 Visits 4 - 7: Day 42 thru 84 (every 14 days +/- 2 days)

The following procedures are performed and data collected at the intermediate visits (every 14 days +/- 2 days until day 84). All information is required.

- Review of concomitant medications, documenting any changes (medication used, route, dose, unit, frequency, indication, start date, stop date or ongoing)
- Wound Assessment
 - Wound size (measured in cm at the longest point and across the widest point, as well as depth)
 - Wound bed appearance
 - Exudate level, colour and consistency
 - Condition of peri-wound skin
 - Maximum pain level on a scale of 0 to 10 within the last 24 hours
 - Level of odour on a scale of 0 to 10 for the study participants and mild/medium/strong for the clinician.
 - Therapeutic Index for Local Infections (TILI) score
- Dressing application Care (required), documentation of any additional products used
- Document any additional therapies
- Document and address Adverse Events
- Document and address Serious Adverse Events
- Number of intermediate visits where dressings were changed between scheduled visits (this is the number of times a subject received a new dressing since the last visit)
- Wound-QOL-14 at the study exit or last visit (Visit 7).

10.5 Unscheduled Visit

Unscheduled visit is any visit that is not a scheduled study visit and is not a pre-planned standard of care clinical visit.

